CooperVision is evaluating the clinical performance of an investigational silicone-hydrogel lens referred to as the Invigor I (test) compared to the clariti lens (control) when worn on a daily wear basis over one-month for each lens type in a randomized, bilateral, cross-over, dispensing study.

[REDACTED]

2 Study Objective

This is a study to evaluate the clinical performance of the Invigor I lens when worn on a daily wear modality over one-month usage.

The primary variables of interest are:

- Lens surface wettability and surface deposits
- Lens fit performance

The secondary variable of interest is:

- Anterior ocular physiological response

[REDACTED]

[REDACTED]

[REDACTED]

3 Study Design

This will be a randomized, multicenter, bilateral, one month cross-over, double-masked, dispensing study comparing the Invigor I test lens against the clariti control lens. Each subject will be randomized to wear either the test or control as a matched pair first with a study duration of approximately two months. Both test and control lenses will be used in a daily wear modality for one month. There will be no planned lens replacement during the course of the one-month study unless due to lens damage/defects. It is anticipated that this study will involve up to 5 visits: Baseline (screening and dispense the first pair visit), 2-week follow-up visit for the first pair, one-month follow-up visit for the first pair and dispense the second pair, 2-week follow-up visit for the second pair, and one-month follow-up visit for the second pair and exit visit.

4 Ethics Review / Statement of Compliance

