3. The lens fit will be assessed for fit acceptance (acceptable or not acceptable) and absence of lens defects. If the fit is acceptable and there are no defects, the subject will be allowed to sit for 10 minutes to allow for the lenses to settle.

4. [REDACTED]

5 [REDACTED]

6 [REDACTED]

7. [REDACTED]

8. Monocular lens surface and fit will then be assessed and graded according to the CVI grading scales (Appendix 2):

[REDACTED]

c. Lens wettability (0-4 scale)

[REDACTED]

f. Lens deposition (0-4) and deposit type

[REDACTED]

9. Monocular lens fit will be assessed and graded according to the CVI grading scales (Appendix 2). Lens fit will be video recorded in the event of poor fit.

[REDACTED]

b. Lens centration (optimal /slightly decentered, <0.5mm /extremely decentered >0.5mm, NTSI)

[REDACTED]

[REDACTED]

[REDACTED]

4. Monocular lens surface will then be assessed and graded according to CVI grading scales (Appendix 2).

[REDACTED]

c. Lens wettability (0-4 scale)

[REDACTED]

f. Lens deposition (0-4) and deposit type

[REDACTED]

5. Monocular lens fit will then be assessed and graded according to CVI grading scales (Appendix 2).

[REDACTED]

b. Lens centration (optimal /slightly decentered, <0.5mm /extremely decentered >0.5mm, NTSI)

[REDACTED]

[REDACTED]

i. Overall lens fit acceptance (0-4 scale, and yes/no) and investigator reason, if unacceptable.

[REDACTED]

[REDACTED]

7. Slit lamp biomicroscopy will be assessed according to the guidelines set out in the CVI grading scales. The same pair of contact lenses will be re-inserted.

8. The subject will be instructed to wear the study lenses for at least 8 hours per day, maximum of 16 hours per day and at least 5 days per week.

9. The subject will be discharged and reminded to return for the one-month visit.

7.4.3 Visit 3: One Month Visit Pair #1 (Day 28 ± 4)/Dispensing pair #2

Subjects will be asked to wear lenses for at least 2 hours prior to the visit appointment.

Subjects who attend without lenses in situ for at least two hours will be rescheduled.

The following procedures will be performed (any ocular measurement procedures outlined below will be carried out on each eye):

[REDACTED]

[REDACTED]

- 1. [REDACTED]
- 2. [REDACTED]
- 3. [REDACTED]
- 4. [REDACTED]
- 5. [REDACTED]
- 6. [REDACTED]
- 7. [REDACTED]
- 8. [REDACTED]
- 9. [REDACTED]
- 10. [REDACTED]
- 11. [REDACTED]
- 12. [REDACTED]
- 13. [REDACTED]
- 14. [REDACTED]
- 15. [REDACTED]

[REDACTED]

- 1. [REDACTED]
- 2. [REDACTED]

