10.2 Statistical analysis

De-identified data will be provided to the sponsor by each site for the sponsor to perform the analyses. Each site will only have access to the data collected at their site.

Summary statistics will be produced (e.g. mean, standard deviation). Non-inferiority testing will be performed as appropriate. Paired t test will be used to compare slit lamp biomicroscopy, lens fit and subjective scores between study lens types. Repeated Measures Analysis of Variance (ANOVA) or paired analysis will be used to compare the variables between study visits. The critical level for statistical significance will be set at $p \leq 0.05$.

All participants who were evaluated will be used in the analysis. In the event of missing data, individual data points will be excluded in the analysis and not extrapolated from the collected data. A detailed statistical analysis plan will be outlined in the report.

11 Data Quality Assurance

[REDACTED]

[REDACTED]

[REDACTED]

[REDACTED]

- [REDACTED]
- [REDACTED]
- [REDACTED]
- [REDACTED]
- [REDACTED]
- [REDACTED]

[REDACTED]

[REDACTED]

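### Section 10.2 names only a paired t test for lens fit, a primary variable with yes/no and three-level items; near 100% acceptance its interval can be too narrow for a non-inferiority claim

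*Combined protocol and SAP*

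**What the plan says.** Section 2 lists "Lens fit performance" among the primary variables of interest. Much of the fit assessment is redacted, but these items are visible:

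- **Dispensing check (7.4.1, step 3), two outcomes:** "The lens fit will be assessed for fit acceptance (acceptable or not acceptable) and absence of lens defects".
- **Centration (7.4.1 and the follow-up visits), three ordered categories:** "Lens centration (optimal /slightly decentered, <0.5mm /extremely decentered >0.5mm, NTSI".
- **Overall acceptance (follow-up visits, including 7.4.3), recorded in two forms:** "Overall lens fit acceptance (0-4 scale, and yes/no) and investigator reason, if unacceptable".

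Section 10.2 names one between-lens test for fit: "Paired t test will be used to compare slit lamp biomicroscopy, lens fit and subjective scores between study lens types". It makes no exception for yes/no or categorical items. It adds "Non-inferiority testing will be performed as appropriate", with no variable, margin, sidedness or interval method, and leaves the detailed analysis plan to the report.

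**The concern.** A paired t interval takes its width from the standard deviation of the within-subject differences. For a yes/no item, that standard deviation depends only on the discordant pairs, that is, subjects whose fit is acceptable on one lens and not on the other. When discordant pairs are few, the estimated standard deviation is unstable and tends to be too small. When there are none, it is zero: the t statistic is 0/0 and the interval is a single point.

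High acceptance is plausible here, because the dispensing procedure continues on this condition: "If the fit is acceptable and there are no defects, the subject will be allowed to sit for 10 minutes". The documents give no acceptance rate, however.

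In a difference test, sparse discordance mostly makes the t test uninformative. In a non-inferiority comparison the interval limit is itself the decision, so too narrow an interval makes it too easy to conclude that the test lens fits no worse than the control.

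**Working it through.** **The plan's own figure.** Table 3 gives 56 and 63 subjects for a mean difference of 0.5, SD 1.3 and p = 0.05. The two-sided paired t test (noncentral t) reproduces both: power is 80.7% at n = 56 and 85.2% at n = 63. A one-sided 5% test would give 44 and 50. The plan's level is therefore two-sided 5%, and I take one-sided 2.5% as the matching non-inferiority level. Table 3 concerns 0-10 subjective ratings and says nothing about the yes/no fit items.

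**Inputs.** From the plan (7.1 and 10.1): n = 60 completing subjects. Assumed, because the plan is silent: one yes/no result per subject, margins of 5 and 10 points, and the discordance rates below. Let b be the number of subjects acceptable on control only and c the number acceptable on test only (reverse discordance).

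**Interval.** Mean difference m = (c − b)/n; variance s² = [(b + c) − n·m²]/(n − 1); limits m ± t(0.975; 59)·s/√n, with t = 2.001.

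Example, b = 1 and c = 0: m = −1/60 = −0.0167; s² = (1 − 1/60)/59 = 0.0167; s/√60 = 0.0167; lower limit = −0.0167 × (1 + 2.001) = −0.0500.

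| Discordant pairs (b, c) | Paired t lower limit | Paired score lower limit (Tango) |
|---|---|---|
| 0, 0 | 0.0 points (zero width) | −6.0 |
| 1, 0 | −5.0 | −8.9 |
| 2, 0 | −8.0 | −11.4 |
| 3, 0 | −10.7 | −13.7 |

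The exact 97.5% upper limit for 0/60 is 1 − 0.025^(1/60) = 6.0%, in line with the score limit.

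**How often no pair is discordant.** If each lens fails independently in a proportion f of subjects, the probability is [1 − 2f(1 − f)]^60. For f = 1% this is 0.9802^60 = 30%; for f = 2% it is 0.9608^60 = 9%.

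**Coverage of the nominal 95% t interval** (exact enumeration, true rates of control-only v test-only acceptance): 70% at 2% v 0%; 83% at 2% v 1%; 92% at 3% v 2%; 98% at 2% v 2%; 95% at 5% v 5%. The shortfall is confined to sparse, one-sided discordance.

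**False non-inferiority.** Set the true deficit equal to the margin and declare non-inferiority when the lower limit lies above minus the margin. With no reverse discordance this can be done by hand:

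- 5-point margin: the t limit passes only when b = 0 (at b = 1 it is −5.002). Error = 0.95^60 = 4.6%. The score limit at b = 0 is −6.0 and fails, so its error is 0%.
- 10-point margin: the t limit passes for b ≤ 2. Error = 0.9^60 + 60(0.1)(0.9^59) + 1770(0.01)(0.9^58) = 0.0018 + 0.0120 + 0.0393 = 5.3%. The score limit passes for b ≤ 1, giving 1.4%.

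Enumeration with reverse discordance, nominal one-sided 2.5%:

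| Reverse discordance | t, 5 points | Score, 5 points | t, 10 points | Score, 10 points |
|---|---|---|---|---|
| 0% | 4.6% | 0% | 5.3% | 1.4% |
| 1% | 6.9% | 1.4% | 4.1% | 2.1% |
| 2% | 6.0% | 1.8% | 3.8% | 2.2% |
| 5% | 3.4% | 2.2% | 3.2% | 2.1% |
| 10% | 2.7% | 2.3% | 2.5% | 2.3% |

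**Centration.** Scored 0/1/2 and simulated with all control fits optimal, the t-based error was 4.6-5.3% at nominal 2.5%. With a wider spread (80/18/2% on control, 70/28/2% on test) it was 2.4%, so there was no inflation.

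**The case against.** The strongest reply is that the word scores in the sentence may govern lens fit as well, so that the t test is meant only for the 0-4 acceptance grade. That reading is possible. Section 10.2 would then name no between-lens test at all for yes/no acceptance or three-level centration, and the same edit would be needed. Other fit items and the grading appendix cannot be seen, so how much of the variable is categorical is unknown.

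Four stronger readings are tempting and are not supported:

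- **That the trial will produce a false non-inferiority finding on fit.** The plan does not tie non-inferiority to fit or to a t interval, and gives neither a margin nor an acceptance rate. What can be shown is a conditional inflation of the error rate.
- **That the error is 14-19%.** Exact enumeration gives 19.2% (5 points) and 13.7% (10 points) at one-sided 5% with no reverse discordance. The plan does not adopt that level, and Table 3 points to two-sided 5%.
- **That the t test also exaggerates ordinary differences.** A 4-0 split gives p = 0.045 by paired t and 0.125 by exact McNemar, but the asymptotic McNemar p is 0.046, so the gap mostly reflects the conservatism of the exact test. In simulation under the null the paired t was not liberal (4.8% with 5% of fits slightly decentered).
- **That failed fits drop out as missing.** Section 10.2 says "In the event of missing data, individual data points will be excluded in the analysis", but step 3 of dispensing records an unacceptable fit as an observed result, all evaluated participants are to be analysed, and the following steps are redacted.

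It is also fair to say that an analyst who found no discordant pair would notice that no t test can be computed. At a 10-point margin such a result would pass under the exact limit as well; the excess error there comes from the case of two discordant pairs.

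**Conclusion.** The concern holds in limited form. The only between-lens test named for a primary variable does not suit two of its visible items, and a better method is available at almost no cost. The consequence depends on sparse discordance. With 60 pairs, assumed margins of 5 to 10 points and 0-2% reverse discordance, a non-inferiority conclusion from the paired t interval would be wrong about 4-7% of the time at nominal 2.5%. At 5% reverse discordance the rate is a little over 3%, and at about 10% it is nominal. All of this assumes one result per subject; fit is graded per eye, and the visible text does not say how the eyes are combined. The point deserves correction before the data are seen, but it does not undermine the trial as a whole.

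**What to change.** In section 10.2:

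1. Limit the paired t test to the graded scores (the 0-4 and 0-10 scales).
2. Compare yes/no fit acceptance with McNemar's test, and report a score-type or exact interval for the paired difference in proportions.
3. Compare centration as optimal v not optimal in the same way, or with a Wilcoxon signed-rank test on the ordered categories.
4. State how the two eyes give one result per subject, since these methods need it.
5. If non-inferiority is to be tested on either item, say so, with the margin and the one-sided level, and base it on the interval in item 2 or its counterpart for dichotomised centration.

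The cost is a few sentences and little extra analysis. Intervals will be slightly wider: with no discordant pair, the lower limit becomes −6.0 points instead of 0.

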7.1 Subjects

This study will recruit at two clinical sites, the Clinical Optics Research Lab (CORL) at Indiana University and UC Berkeley Clinical Research Center (CRC). Up to 80 subjects will be dispensed across both sites with the aim of completing 60 subjects across both sites. Each subject will be given a unique ID number. Subject ID numbers will be assigned to the subjects sequentially and in ascending order, and will not be reused in the event of screen failure, subject dropout or discontinuation from the study.

Potential subjects will be identified from the investigators' clinic and research database records and/or will be actively recruited by advertisements circulated at the investigational sites as approved by the appropriate IRB.

There are no provisions for replacing subjects during the study who are discontinued from the study.

Additionally, all subjects must meet the study inclusion and exclusion criteria listed below.

Inclusion Criteria

A person is eligible for inclusion in the study if he/she:

- Has had a self-reported oculo-visual examination in the last two years.
- Is at least 18 years of age and has full legal capacity to volunteer.
- Has read and understood the information consent letter.
- Is willing and able to follow instructions and maintain the appointment schedule.
- Is correctable to a visual acuity of 20/40 or better (in each eye) with their habitual vision correction or 20/20 best-corrected.
- Currently wears soft contact lenses.
- Requires spectacle lens powers between -0.75 to -6.50 diopters sphere (0.25D steps).
- Has no more than 0.75 diopters of refractive astigmatism.
- Has clear corneas and no active ocular disease.
- Has not worn lenses for at least 12 hours before the examination.
- Has a usable pair of spectacle lenses if required for transportation to the site for the initial visit

Exclusion Criteria

A person will be excluded from the study if he/she:

- Has never worn contact lenses before.
- Has any systemic disease affecting ocular health.
- Is using any systemic or topical medications that will affect ocular health.
- Has any ocular pathology or severe insufficiency of lacrimal secretion (moderate to severe dry eyes) that would affect the wearing of contact lenses.
- Has persistent, clinically significant corneal or conjunctival staining using sodium fluorescein dye.
- Has any clinically significant lid or conjunctival abnormalities, active neovascularization or any central corneal scars.
- Is aphakic.

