7.4.1 Visit 1: Screening / Baseline Visit / Dispensing Pair #1

Screening / Baseline

The following evaluations will be performed to assess eligibility according to the Inclusion and Exclusion Criteria at the Screening visit:

1. The subject is expected to attend the screening / baseline visit not wearing their habitual contact lens products for at least 12 hours prior to the study visit.
2. The subject will be required to read and sign an Informed Consent Form prior to enrolment. When the subject has signed the consent form, the subject will be considered to be enrolled on to the study.
3. Subject demographics and medical history (age, sex, race and ethnicity, medical conditions, medications, allergies) will be recorded by the investigator
4. Contact lens history (own lens information, rewetting drop use, and wear time)

5. Baseline monocular high illumination, high contrast (HIHC) entrance visual acuity with habitual spectacles or spectacle refraction
6. Auto refraction/auto keratometry: Flat and Steep K readings (D)
7. Sphero-cylindrical refraction (D), and best sphere refraction (D) & monocular & binocular distance visual acuity (HIHC) (logMAR)
8. The endpoint of this over refraction will be the best objective acuity, with (-) only being given with objective acuity, not subjective acuity improvement (not to the point that the letters start to shrink in size).

[REDACTED]

[REDACTED]

11. Slit lamp biomicroscopy will be assessed according to the guidelines set out in the CVI Grading scales (Appendix 2).
12. The investigator will confirm that the subject meets the criteria set out in the inclusion criteria, and none of the exclusion criteria and is eligible to continue in the study.
13. The subject will be assigned a randomization ID and the first pair of contact lenses (either test or control) will be selected according to the randomization table.
14. Initial contact lens power chosen based on vertexed, spherical equivalent obtained from refraction. The contact lens power will be kept the same for both test and control.
15. The contact lenses will be dispensed by a research assistant / study coordinator / technician (in a manner which does not unmask the subject and investigator).

Dispensing Pair #1

1. The lenses will be inserted by the subject from the blister pack. The use of saline for rinsing prior to insertion is permitted if necessary.

[REDACTED]

[REDACTED]

[REDACTED]

[REDACTED]

[REDACTED]

[REDACTED]

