8.4 Discontinuation from the Study

A subject's study participation may be discontinued at any time if, in the opinion of the sponsor or the investigator it is in the best interest of the subject. All discontinuations will be fully documented on the appropriate study forms and the Discontinuation Form will be completed.

9 Device Malfunctions

A device malfunction means the failure of the device to meet its performance specification or otherwise perform as intended. *Any defective lens that is likely to cause or contribute to a Serious Adverse Event should be reported to the Principal Investigator and the sponsor **within 24 hours** of the investigator becoming aware of the malfunction.*

Other defective lenses should be reported to the sponsor as soon as possible.

This clinical study will also ascertain satisfaction or preference with subjective attributes such as comfort, vision, or lens handling. Responses to these subjective questionnaires will not be considered as complaints or Device Malfunctions.

10 Statistical Analysis

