10.1 Sample size

Approximately 80 subjects will be enrolled with a goal that approximately 60 will be completed. Based on historical clinical data a sample size of 60 completing subjects is sufficient to detect a mean difference of 0.5 (0 – 10) in subjective ratings assuming $\alpha=0.05$ and a power of 80% (Table 3).

Table 3: Sample Size Calculations

Mean individual difference in score	Mean individual standard deviation	Sample size, Power 80% ($p = 0.05$)	Sample size, Power 85% ($p = 0.05$)
0.5	1.3	56	63

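### The paired t test in section 10.2 is a complete-pair analysis, so it cannot use all evaluated participants, and lens-related loss could bias the one-month lens comparison, most plausibly towards no difference

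*Combined protocol and SAP*

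**What the plan says.** Section 10.2 sets the analysis population: "All participants who were evaluated will be used in the analysis". It then names the between-lens method: "Paired t test will be used to compare slit lamp biomicroscopy, lens fit and subjective scores between study lens types". Missing values are left out point by point, with no imputation. Repeated measures ANOVA appears only for comparing visits. Non-inferiority testing is mentioned without a margin or endpoint, and the detailed analysis plan is deferred to the report.

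On numbers, section 7.1 says "Up to 80 subjects will be dispensed across both sites with the aim of completing 60 subjects across both sites" and makes no provision for replacing subjects who discontinue. Section 10.1 says "Approximately 80 subjects will be enrolled with a goal that approximately 60 will be completed".

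On leaving, section 8.4 reads "A subject's study participation may be discontinued at any time if, in the opinion of the sponsor or the investigator" judges this to be in the subject's best interest. It requires a Discontinuation Form. Section 10 plans no summary of discontinuations by lens or reason.

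**The concern.** In a two-period crossover, a paired t test at a given visit uses only subjects with a value on both lenses at that visit. The statement about all evaluated participants therefore does not describe the between-lens comparison, and no rule says how a subject with data on one lens enters it.

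This matters if loss is related to the lens, and the protocol contains routes by which it could be. Section 7.4 allows a follow-up lens assessment only when the subject attends wearing the study lenses, and sections 7.4.3 to 7.4.5 ask for two hours of wear beforehand. Adverse event codes 17 and 24 in section 8.1 cover signs or symptoms that interrupt lens wear. A subject who does badly on a lens may thus lack that lens's one-month value and drop out of the one-month pair altogether. Lens fit is a primary variable and anterior ocular response the secondary one (section 2), and both are to be compared by this test. Shrinkage of a real difference would favour a non-inferiority conclusion.

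**Working it through.** **1. The plan's own figure.** Inputs from section 10.1, Table 3: difference 0.5, SD 1.3, alpha 0.05. A paired t test, two-sided, using the noncentral t distribution gives n = 55.01, rounded up to 56, at 80% power, and 62.64, rounded up to 63, at 85%. Both match Table 3. The normal approximation at 80% is ((1.960 + 0.842) × 1.3 / 0.5)² = 53.1. Power is 83.4% with 60 pairs and 92.5% with 80. Loss unrelated to the lenses is therefore already covered; the issue is bias, not power.

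**2. The allowance.** (80 − 60) / 80 = 25%.

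**3. Who gives a pair, and when.** Pair 2 is graded at dispensing (section 7.4.3, repeating 7.4.1), at two weeks (7.4.4) and at one month (7.4.5).

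| Subject leaves | Dispensing pair | Two-week pair | One-month pair |
|---|---|---|---|
| Before pair 2 is dispensed | no | no | no |
| After that, before Visit 4 | yes | no | no |
| After Visit 4, before Visit 5 | yes | yes | no |
| Completes | yes | yes | yes |

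**4. Size when leaving follows a bad two-week grade.** Assumptions, none from the documents: 80 subjects; higher grade is worse; between-subject SD 0.5, subject-by-period SD 0.4, residual SD 0.3; a subject leaves after a high two-week grade on whichever lens is worn.

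| Loss (about 25% in total) | True 0.30: paired estimate | True 0.50: paired estimate |
|---|---|---|
| All driven by the grade | 0.264 to 0.266 | 0.440 to 0.441 |
| 10% of subjects driven by the grade, rest random | 0.281 | 0.474 |
| 5% of subjects driven by the grade, rest random | 0.287 | 0.484 |

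Relative bias:
- All driven by the grade: (0.30 − 0.264) / 0.30 = 12% and (0.50 − 0.440) / 0.50 = 12%.
- 10% driven: 0.019 / 0.30 = 6% and 0.026 / 0.50 = 5%.
- 5% driven: 0.013 / 0.30 = 4% and 0.016 / 0.50 = 3%.

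In the heaviest case, a mixed model on all observed visits gave 0.306 and 0.509 without a period term (100 trials). With a period term it gave 0.29 and 0.50 (60 trials, simulation error about 0.01).

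**5. Sensitivity to the mechanism.** Table 3 scale: true difference 0.5, SD of the difference 1.3. Assumed: within-subject correlation 0.3 to 0.7, and 20 of 80 lost.

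| Who leaves | Mean paired difference | Power |
|---|---|---|
| Random | 0.50 | 82–85% |
| Worst on the first lens, whichever it is | 0.45–0.48 | 79–83% |
| Worst on either lens | 0.37–0.43 | 72–77% |
| Worst on the poorer lens only | 0.18–0.28 | 21–40% |
| Worst on the better lens only | 0.71–0.82 | not needed: the difference grows |

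**The case against.** A reader might infer that the difference will shrink by a known amount. The documents do not support that: they give no dropout rate by lens or by reason, and step 5 shows that the bias can be nil or reversed. A reader might also take the 25% as expected lens-related loss. It is only an allowance: section 7.1 sets an upper limit on subjects dispensed and an aim for completers, while section 10.1 counts subjects enrolled. Section 7.4.1 defines enrolment by consent ("When the subject has signed the consent form, the subject will be considered to be enrolled on to the study"), so the section 10.1 count may include screen failures. Out-of-window visits, treated as unscheduled under section 7.4, are a further loss with no stated link to lens performance.

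Nor does every subject who leaves disappear from every comparison. Those who leave during pair 2 keep dispensing pairs and perhaps two-week pairs, and section 10.2 names no single visit for the lens comparison. Its missing-data sentence can be read as describing an available-data analysis, in which one-lens subjects still enter the summary statistics. The non-inferiority consequence is conditional too, since no margin or endpoint is given.

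On size, even the heaviest case at a true 0.30 moves the estimate by 0.30 − 0.266 = 0.034, about 0.4 of a standard error of 0.088. The leaving rule in step 4 also favours the mixed model, because it depends on a recorded grade. When leaving depended on the unrecorded one-month grade, the mixed model gave 0.277 for a true 0.30 (simulation error 0.011).

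All of this limits the certainty and size of the point. What remains is that the named test is a complete-pair analysis, that no rule covers one-lens subjects, and that recorded two-week grades go unused in the one-month comparison.

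**Conclusion.** The point holds in conditional form. The statement on population and the named test do not agree for the between-lens comparison. If leaving is linked to poor performance of the lens then worn, bias towards no difference is the most plausible result. Its size is about 12% if the whole 25% loss arises from bad two-week grades, and about 3 to 6% if 5 to 10% of subjects leave for that reason. The deliberate extremes in step 5, with all losses tied to one lens, run from a large shrinkage to a clear inflation. All these sizes rest on assumed SDs, correlations and leaving rules. The change is worth making before unmasking, because the method is a concrete improvement that uses data already planned for collection.

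**What to change.** In section 10.2:

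- Make the between-lens analysis of graded variables a linear mixed model on all observed two-week and one-month grades. Use fixed effects for lens, visit, lens-by-visit, period and sequence, and random effects for subject and subject-by-period. Report the one-month lens contrast from it. Period and sequence are needed because one-lens subjects add between-subject information, and unequal loss between periods could otherwise let a period effect into the lens estimate.
- Keep the paired t test as a completer sensitivity analysis, and state which subjects form its paired set at each visit.
- Tabulate discontinuations by lens worn and by the reason on the Discontinuation Form.
- As a sensitivity analysis for yes/no fit acceptance, count a discontinuation recorded as due to the lens worn as a failure for that lens. Section 8.4 does not say whether the form records this, so that should be confirmed.

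The cost is wording and a little more analysis. No new measurements are needed and nothing is imputed for the graded variables. The model assumes that the recorded grades explain who leaves (missing at random), so it reduces the bias but may not remove it.

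### Non-inferiority would be judged on all evaluated subjects only; for outcomes that depend on wear, a per-protocol analysis should stand beside it

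*Combined protocol and SAP*

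**What the plan says.** Section 10.2 contains two statements that need to be read together: "Non-inferiority testing will be performed as appropriate" and "All participants who were evaluated will be used in the analysis". It names no endpoint, margin or one-sided level for the non-inferiority test. The readable text defines no per-protocol set, no adherence criterion for analysis and no sensitivity analysis, and 10.2 leaves the detailed analysis plan to the report.

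The between-lens method that is named is a difference test: "Paired t test will be used to compare slit lamp biomicroscopy, lens fit and subjective scores between study lens types". Section 10.1 is also written for a difference: "a sample size of 60 completing subjects is sufficient to detect a mean difference of 0.5" on a 0–10 subjective rating.

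The wear schedule appears in the Visit 2 procedures (step 8, just before 7.4.3) and is repeated for the second pair through 7.4.4. Subjects are told to "wear the study lenses for at least 8 hours per day, maximum of 16 hours per day and at least 5 days per week". Nothing readable links this to the analysis.

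Two rules do limit what is analysed. Under 7.4.3 to 7.4.5, a subject who has not had the lenses in for two hours is rescheduled. Under 7.4, a visit outside its window is treated as unscheduled in the analysis.

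**The concern.** Using everyone evaluated is usually the cautious choice for a difference test, because poor adherence makes a difference harder to show. For non-inferiority the direction reverses: anything that makes the two lenses look alike helps the claim.

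The primary variables in Section 2 include surface wettability and deposits, and the secondary variable is the anterior ocular physiological response. These plausibly depend on accumulated wear. A subject who seldom wore either pair may return two similar sets of grades. Neither the two-hour rule, which governs the visit day, nor the window rule, which governs timing, removes such a subject.

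At stake is a conclusion that the test lens is no worse than the control when, in subjects who wore both as instructed, it is worse by the full margin. Nothing in the readable plan would bring this to light.

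**Working it through.** **1. The plan's own figure.** Inputs from 10.1, Table 3: difference 0.5, SD of individual differences 1.3, alpha 0.05. For a paired t test at two-sided 0.05, the noncentrality is δ√n/SD. The smallest n reaching the target power is 56 for 80% (power 80.7%) and 63 for 85% (power 85.2%), so Table 3 reproduces exactly. One-sided 0.05 would give 44 and 50, which do not match. Table 3 is therefore a two-sided difference calculation. At n = 60, 0.5 × √60 / 1.3 = 2.98 and power is 83.4%.

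**2. Dilution model.** Not in the documents, hence assumed:
- margin M of 0.25, 0.5 or 1.0 (0.5 is the plan's detectable difference, not a stated margin);
- one-sided level 0.025;
- a share f of subjects with a true lens difference of zero.

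Let the true deficit of the test lens in adherent subjects equal M, so that any non-inferiority finding is false. Then:
- mean deficit among all evaluated = (1 − f)M;
- SD_f = √(1.3² + f(1 − f)M²);
- noncentrality = fM√60 / SD_f;
- false-pass rate = the chance that a noncentral t on 59 df exceeds 2.001.

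Worked case, M = 0.5:
- f = 10%: SD_f = √(1.69 + 0.0225) = 1.309; noncentrality = 0.05 × 7.746 / 1.309 = 0.296; rate 4.8%.
- f = 20%: SD_f = √(1.69 + 0.04) = 1.315; noncentrality = 0.10 × 7.746 / 1.315 = 0.589; rate 8.4%.

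Simulation with 100,000 trials gave 4.8% and 8.4%.

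| Assumed margin | f = 0 | f = 10% | f = 20% |
|---|---|---|---|
| 0.25 | 2.5% | 3.5% | 4.8% |
| 0.5 | 2.5% | 4.8% | 8.4% |
| 1.0 | 2.5% | 8.2% | 20.1% |

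Zero difference is the extreme case. If the low-wear subjects kept half the difference, 20% of them would shift the mean by 0.20 × 0.5 × M = 0.10M, the same as 10% with none.

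**3. Scale.** The SD of 1.3 belongs to 0–10 subjective ratings. Wettability and deposits are graded 0–4, and no SD is given for them. The rates depend on f and on M/SD, so the three rows correspond to ratios of about 0.19, 0.38 and 0.77. They carry over to another scale only at the same ratio.

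**4. After the fix.** If adherence is unrelated to outcome, dropping the diluted subjects returns the per-protocol rate to 2.5%. The cost is power. With M = 0.5, true difference zero and one-sided 0.025:

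| Subjects excluded | Per-protocol n | Per-protocol set alone | Both sets must pass |
|---|---|---|---|
| none | 60 | 83.4% | 83.4% |
| 10% | 54 | 79.2% | about 77% |
| 20% | 48 | 74.2% | about 72% |

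The last column is from 400,000 simulated trials of 60 normal differences (mean 0, SD 1.3), testing all 60 and then the retained 54 or 48, and counting trials in which both passed.

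**The case against.** The strongest reply is that the point corrects a test the plan has not yet defined. Non-inferiority is only an option, the named comparison is a paired t test, and the sample size is for a difference. That stands: the missing endpoint and margin are the more basic gap, and a rule that two sets must agree means nothing until they are filled. Filling them would not settle this point, since any margin would still be tested on the same set.

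Four stronger readings are tempting, and the documents do not support them.

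- *Subjects count however little they wore the lenses.* The two-hour and window rules set a floor. They do not enforce the daily and weekly schedule between visits.
- *The pull towards zero is certain and covers every primary variable.* Fit is graded with the lens on the eye, already at dispensing, so home wear has little bearing on it. For conjunctival staining, the note in 8.1 expects a high level with the control; dilution there would shrink the control's disadvantage, which is no route to false non-inferiority. If wear is cut because one lens performs badly, the simple model need not apply, and a wear-based set then selects on outcome and can itself hide inferiority.
- *The wide range of permitted wear shows the problem.* Over a one-month visit window, compliant wear runs from 24 × 5/7 × 8 = 137 hours to 32 × 16 = 512 hours. All of it follows the instruction, so every such subject would stay in a per-protocol set.
- *Wear time is not collected.* Much of the visit procedure is redacted, and 11.4 mentions take-home questionnaires. Nothing can be inferred from the absence of a readable wear-time item.

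**Conclusion.** The point holds as a limited one. In the readable plan, all evaluated participants are the only set on which non-inferiority could be judged. For deposits, wettability and slit lamp findings, low wear of both lenses can favour the claim, and no planned analysis would show it.

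A reader might infer that this trial's false non-inferiority rate is about 5% to 8%. The documents do not support any single figure. The range from 3.5% to 20.1% rests on an assumed margin, an assumed 10% to 20% of subjects with no lens difference at all, one-sided 2.5%, and an SD borrowed from subjective ratings. Only the direction is firm, and only where the outcome depends on wear, the test lens is truly worse, and under-wear affects both lenses alike.

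This is a worthwhile, inexpensive improvement to the plan. It does not show that the planned analysis is invalid.

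**What to change.** Before unmasking, amend 10.2 as follows for each endpoint on which non-inferiority may be claimed.

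1. Name the endpoint, the margin and the one-sided level.
2. Define a per-protocol set: subjects who meet the criteria in 7.1, followed the protocol's existing wear instruction on both pairs, and had both one-month visits in window.
3. Report this analysis beside the all-evaluated one, and claim non-inferiority only if both meet the margin.
4. Tabulate wear hours and days by lens, with the number of subjects excluded for wear on each lens. Selective under-wear of one lens would then be visible, and the reader could judge whether the exclusions are related to outcome.

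The cost is one more run of the same analysis and, if it is not already collected, a wear-time item for each pair. Some power is lost: at a margin of 0.5 and a true difference of zero, from 83% to about 77% with 10% excluded, or about 72% with 20% excluded, when both sets must pass. Section 7.1 does not allow discontinued subjects to be replaced, so this loss should be weighed when the margin is chosen.
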